The intent-to-treat (ITT) population will include all the subjects after randomization and who received esketamine or placebo during surgery. After randomization, it is assumed that all participants have been administered a placebo or esketamine. The modified intent-to-treat population will be excluded from the analysis after randomization situations no longer meet the eligibility criteria, patients who do not have surgery, or patients who cannot undergo follow-up due to surgery-related complications, such as aphasia or coma. The modified ITT population will be tested for demographic characteristics and efficacy and safety outcomes. The population will be used for primary analysis of the efficacy and safety outcomes.

Per-Protocol population

The per protocol (PP) population will comprise all participants except subjects who are confirmed as protocol transgressors. The subjects excluded from the PP population will be confirmed before being blind. This population was used for sensitivity analysis to determine the effect of missing data. In the PP population, subjects will be analysed according to the treatment received and the real events after postoperative assessments.

8. Statistical considerations

The data will be analyzed by Stata 16.0 software (Stata Corp LP, College Station, TX,

USA) and all significance tests will be two-sided, with an alpha setting of 0.05 and 95% confidence intervals confirmed.

Subgroup analysis

The rate of postoperative 3-day remission will be presented at each level of the variables listed below. The degree of change in the treatment effect of each subgroup at different levels will be evaluated via an interaction test.

Multiplicity

The single primary outcome was defined in the protocol, and all other efficacy variables were treated as secondary or other. The only comparison of interest in this study was between esketamine and placebo, and there was no need to adjust for multiple comparisons. All estimates of treatment effects for secondary endpoints will be presented with 95% confidence intervals, no inferential tests will be performed, and only exploratory tests with simple descriptions of these endpoints will be performed.

Missing Data

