If the amount of missing data is lower than the prescribed attrition rate, which is 10%, the data will drop out. Missing data during the assessment period will be replaced with negative results before breaking blind. Sensitivity analysis will be applied for the different imputation methods, such as imputation with means or medians or dropouts or negative results. The missing data will be reported and analysed to determine their effects on primary efficacy.

9. Statistical analysis

General statistical calculations

For binary outcomes, the summary statistics are reported as the number and proportion, and the χ^2 test was used for hypothesis testing. For outcomes measured on a continuous scale, the summary statistics are reported as the mean and standard deviation (SD) or median and interquartile range (IQR) depending on normality according to the Shapiro-Wilk test. Statistical inference to evaluate the effect of

treatment was presented as absolute mean differences and 95% CIs via the independent t test and linear regression for continuous variables, except skewed variables, for which the absolute difference and 95% CIs were calculated via the Mann-Whitney U test and the Hodges-Lehmann method. All the summarized descriptive statistics will be presented to one further decimal place unless otherwise specified. P values are rounded to 3 decimal places (those less than 0.001 are displayed as <0.001).

Follow-up data

The CONSORT flow chart will be used to summarize the follow-up of patients throughout the trial. Each center records the details of all randomization, intervention, and missing data.

Demographic and baseline characteristics

The demographic information, such as age, sex, weight, height, and body mass index, will be summarized and presented to the participants in the two intervention groups. Other variables included education level, marital status, American Society of Anesthesiologists physical status classification, Charlson's comorbidity index, smoking history, and comorbidity history. Baseline data for operation characteristics, such as delayed extubation, type and extent of resection, and time to spontaneous respiration, will also be obtained.

Efficacy analyses

All statistical analyses for the main effects were two-sided at P values less than 0.05.

Primary efficacy analysis

The primary outcome was postoperative 3-day remission events assessed by the MADRS scale after intervention.

Main Model

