The remission rate of depressive symptoms at 3 days postoperative will be summarized by treatment group via the chi-square test or Fisher's exact test to compare the differences between groups in the m-ITT population. The risk ratio for the intervention comparison is presented, and the 95% CI is reported. The results are

also displayed graphically on a histogram plot.

Secondary efficacy analysis

All secondary endpoints are based on the m-ITT population. For categorical variables, which are presented as frequency counts and percentages, a two-sided Pearson's χ^2 test or Fisher's exact test will be used, as appropriate. The odds ratios and 95% CIs were calculated. For continuous variables, prior to performing the statistical analysis, the assumptions of normality and homogeneity of variance of the residuals of quantitative variables were tested via the Shapiro-Wilk test and Levene's test, respectively. For efficacy analysis, a t test (normal variables) or the Mann-Whitney U test (skewed variables) will be used, as appropriate. The absolute difference and 95% CIs were calculated via the Mann-Whitney U test and the Hodges-Lehmann method.

Safety analysis

Safety endpoints will be assessed in the total population. The related variables are presented as frequency counts and percentages in both the esketamine group and the control group, odds ratios and 95% CIs.

Interaction with subgroups

A summary forest plot will be presented on the basis of the predefined subgroups, and interactions between them will be investigated for the primary endpoint. Exploratory subgroup-specific summary statistics and p values for interactions are presented. A separated logistic model was applied for interaction to identify its effect significance. The subgroup analysis included the following covariates: unbalanced baseline variables, age, sex, severity of depressive symptoms and pain severity after surgery.

Main results with Tables

Table 1. Demographic and preoperative characteristics of the total population.

Characteristics	Esketamine group	Control group
Sex		
Female	n (%)	n (%)
Male	n (%)	n (%)
Age, yr,	Mean (SD)/median (IQR)	Mean (SD)/median (IQR)
Height, cm,	Mean (SD)/median (IQR)	Mean (SD)/median (IQR)
Weight, kg,	Mean (SD)/median (IQR)	Mean (SD)/median (IQR)
Education	n (%)	n (%)
Married	n (%)	n (%)
Living state (alone)	n (%)	n (%)
Employed	n (%)	n (%)
Currently smoke	n (%)	n (%)
Alcohol intake		
Never	n (%)	n (%)
Occasional	n (%)	n (%)

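### The primary efficacy set drops dosed patients whom surgical complications make unassessable, and the SAP gives two missing-outcome rules without saying which is primary

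*SAP*

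**What the plan says.** **Efficacy population.** SAP 7 first defines an ITT set: "The intent-to-treat (ITT) population will include all the subjects after randomization and who received esketamine or placebo during surgery". It then describes a modified ITT (m-ITT) set that removes three groups: patients who "after randomization situations no longer meet the eligibility criteria", patients who have no surgery, and "patients who cannot undergo follow-up due to surgery-related complications, such as aphasia or coma". Of the m-ITT set it says: "The population will be used for primary analysis of the efficacy and safety outcomes". SAP 9 (Main Model) confirms this; the chi-square or Fisher test is used "to compare the differences between groups in the m-ITT population". Secondary endpoints use the same set. The ITT principle is invoked only for the interim analysis (Protocol, Interim analysis; SAP 6).

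**Per-protocol set.** SAP 7 says: "This population was used for sensitivity analysis to determine the effect of missing data". In it, "subjects will be analysed according to the treatment received and the real events after postoperative assessments".

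**Missing outcomes.** SAP 8 says: "If the amount of missing data is lower than the prescribed attrition rate, which is 10%, the data will drop out". The next sentence, with no condition attached, replaces missing assessments with negative results before the blind is broken. A sensitivity list follows (means, medians, dropouts, negative results) that names neither a base case nor a population. The Protocol (Statistical analysis) instead lists mean or median, last observation and multiple imputation.

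**Safety population.** SAP 7 assigns safety to m-ITT. SAP 9 (Safety analysis) assigns it to the total population, which SAP 7 defines as everyone screened with a database record.

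**The concern.** The Protocol starts the infusion while the incision is being sutured. Whether a patient is too aphasic or comatose to be rated on day 3 is known only later, even though some of the causal injury may precede the drug. The exclusion therefore depends on a post-treatment event. The Protocol's Introduction itself says that ketamine may alter intracranial pressure and haemodynamics, and that it is uncertain whether this applies to a single esketamine dose in these patients. A link with treatment cannot be ruled out. The eligibility clause carries no timing, so it could also remove dosed patients.

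If such losses differ by arm, the primary comparison can move either way, and no planned final analysis clearly shows by how much. The interim stopping decision and the final test may also rest on different sets of patients.

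The missing-outcome rules raise a more basic problem. Two rules that give different p-values both stand in the text, and nothing says which one decides the trial.

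**Working it through.** **Inputs.** SAP 5: remission 19.3% versus 10%, 1:1 allocation, two-sided 0.05, 80% power, 506 evaluable, 10% attrition, 564 in total. The documents give no complication count and no split by arm, so every loss figure below is an assumption.

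**The plan's own figure.** The two-proportion formula gives 226 per arm (452) uncorrected and 247 per arm (494) with continuity correction. Multiplying by an interim inflation of 1.018 gives 494 × 1.018 = 503, close to 506. Attrition: 506 / 0.9 = 562.2, so 563, or 564 with equal arms. The sample size is not in dispute. I use 564 / 2 = 282 per arm and, for simplicity, a single look at 0.05.

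**Do the listed analyses restore the excluded patients?**
- ITT set: contains them, but no final analysis is assigned to it.
- Per-protocol set: may contain them, but it uses actual assessments, which they lack.
- Sensitivity list in SAP 8: states no population.

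**Effect of the m-ITT exclusion alone.** The test is the uncorrected chi-square, z = (x₁/n₁ − x₂/n₂) / √[p̄(1−p̄)(1/n₁+1/n₂)]. Excluded patients count as non-remitters when kept.
- All kept: 43/282 = 15.25%, 28/282 = 9.93%, p̄ = 71/564 = 12.59%, SE = 0.02794, z = 1.904, p = 0.0569.
- Four esketamine patients excluded: 43/278 = 15.47%, p̄ = 71/560 = 12.68%, SE = 0.02812, z = 1.969, p = 0.0489. Three exclusions give 0.0508, so four is the smallest number that crosses 0.05.

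| Remitters (esk : plac) | Excluded (esk : plac) | p |
|---|---|---|
| 43 : 28 | 0 : 0 | 0.057 |
| 43 : 28 | 4 : 0 | 0.049 |
| 43 : 28 | 14 : 0 | 0.033 |
| 43 : 28 | 7 : 7 | 0.056 |
| 43 : 28 | 0 : 14 | 0.093 |
| 44 : 28 | 0 : 0 | 0.044 |
| 44 : 28 | 0 : 5 | 0.053 |

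**Effect of the SAP 8 rule.** Suppose the two sentences form one conditional rule with all 564 as denominator (the SAP states none). Then 56/564 = 9.9% missing is dropped and 57/564 = 10.1% is counted as negative. With 56 missing:

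| Remitters (esk : plac) | Missing (esk : plac) | p, dropped | p, negative |
|---|---|---|---|
| 43 : 28 | 30 : 26 | 0.047 | 0.057 |
| 43 : 28 | 28 : 28 | 0.055 | 0.057 |
| 43 : 28 | 26 : 30 | 0.065 | 0.057 |

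Near the design rates (50 versus 28), with 28 missing split 22:6, p is 0.003 dropped and 0.007 negative; nothing changes.

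**Long-run behaviour.** Simulation of 1,000,000 trials, 282 per arm. Repeat runs agree to about 0.1 percentage point.

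True effect of 19.3% versus 10% among assessed patients, loss unrelated to remission:

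| Loss (esk : plac) | Power, dropped | Power, negative | Rules disagree |
|---|---|---|---|
| 5% : 5% | 87% | 87% | 1.6% |
| 8% : 2% | 87% | 79% | 7.9% |
| 2% : 8% | 87% | 92% | 5.3% |
| 9.9% : 9.9% | 85% | 84% | 2.5% |
| 13% : 7% | 85% | 76% | 9.2% |

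At 8%:2% essentially every disagreement is significant only when data are dropped; at 2%:8% it is the reverse.

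No effect, 10% remission in both arms, type I error:

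| Who is lost | Loss (esk : plac) | Dropped | Negative |
|---|---|---|---|
| Only non-remitters | 8% : 2% | 5.8% | 5.0% |
| Only non-remitters | 10% : 0% | 7.1% | 5.0% |
| Unrelated to remission | 8% : 2% | 5.0% | 5.7% |
| Unrelated to remission | 10% : 0% | 5.0% | 6.9% |

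Neither rule controls error better in general; it depends on why patients are lost.

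**The case against.** The strongest reply is that SAP 8 can be read as one rule: drop below 10%, otherwise count as negative. One database would then give one p-value, with the cut-off fixed in advance. But the SAP has no word for otherwise, both methods reappear as sensitivity options, and no denominator is given. Even on this reading, the primary method switches on observed missingness at the attrition rate the trial plans for.

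It is also fair to say that the m-ITT exclusion is pre-specified, that populations are fixed before unblinding, that a CONSORT chart is planned, and that both contested analyses would probably be reported. Blind fixing prevents selective decisions. It does not remove bias from exclusions that depend on post-treatment events, and reporting two results does not say which is primary. Multiple imputation may not have been withdrawn, since the SAP is to be used together with the Protocol, but the SAP does not name it.

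Three points stand. The examples that cross 0.05 are tables placed beside that line with lopsided losses; neutral splits barely move p. Counting missing as negative has its own costs in error rate and power. And the population and safety points do not in themselves make the primary p-value ambiguous; that comes from SAP 8.

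**Conclusion.** The concern holds, and it must be fixed before unblinding. The decisive defect is that the primary result is not uniquely defined: SAP 8 supports two analyses of the same data. The m-ITT exclusion adds a possible bias of unknown direction that no final efficacy analysis clearly exposes. The safety population is contradictory as written.

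The size is conditional. It rests on assumed losses, a single look at 0.05 and 282 per arm. With balanced loss, or an effect near the planned one, the conclusion is unlikely to change. With a borderline result, four one-sided exclusions are enough to cross 0.05. With loss of 8%:2%, the two missing-outcome rules disagree in about 8% of trials.

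**What to change.** - **Primary set.** Use the ITT set that SAP 7 already defines, made explicit: all randomised patients in whom the infusion was started, analysed as randomised (the last two conditions are additions to the SAP text). Exclude only for no surgery or no study drug, decided blind. Use the same set at interim and final.
- **Missing day-3 outcome.** Delete the 10% switch and name one primary rule that applies whatever the amount missing. Counting an unassessable or missing MADRS as non-remission is the natural choice, because the SAP already states it and it keeps every dosed patient. Present it as part of the outcome definition, not as a guarantee of error control.
- **Sensitivity analyses.** Specify complete cases (close to the present m-ITT), the Protocol's multiple imputation, and an analysis that varies the assumed remission of unassessed patients separately by arm.
- **Reporting.** In the planned CONSORT chart, show excluded and unassessed patients by arm with reasons.
- **Safety.** Reconcile SAP 7 and SAP 9 on one safety population.

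The cost is SAP wording and a little extra analysis, with no additional patients. Remission rates fall slightly in both arms. Single-look power is 84% rather than 85% at 9.9% loss in each arm. It would fall to 79% (8%:2%) or 76% (13%:7%) if loss were heavier on esketamine, and rise to 92% at 2%:8%.

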To compare all the safety events of surgery and study drugs administered intraoperatively in terms of psychiatric symptoms, dissociative symptoms and manic

symptoms, and adverse and serious adverse events during the study period. Further exploratory objectives were to evaluate the postoperative 1-, 3-, and 6-month quality of life (WHODAS 2.0) and depressive symptoms.

Study endpoints

Primary efficacy

The remission rate of depressive symptoms at 3 days postoperatively was defined as a Montgomery-Åsberg Depression Rating Scale (MADRS) score less than or equal to 10. [2]

Secondary efficacy

The remission rate of depressive symptoms at discharge was defined as MADRS scores less than or equal to 10.

The response rates of depressive symptoms 3 days after surgery and at discharge.

The rate of moderate-to-severe pain during the first postoperative 3 days and severe pain were defined as numeric analogue scale (NAS) scores greater than 3.

Changes in further efficacy: Changes in depressive symptom scores at 1 month, 3 months, and 6 months postoperative; and the WHODAS 2.0.

Safety efficacy

Psychiatric complications: drug-related manic, psychotic, and dissociative symptoms during the first 3-day postoperative period. [3,4]

Surgery-related complications

3. Study overview

This study is a multicenter, randomized, placebo-controlled and double-blinded clinical trial. The primary null hypothesis of this study is that there is no difference in the 3-day postoperative remission rate between 0.2 mg/kg esketamine administered intraoperatively for 40 min and placebo administered at the same time in the same volume.

Patients undergoing major surgery, combined with moderate-to-severe depressive symptoms defined as those with a Patient Health Questionnaire 9 (PHQ-9) [5] score

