Patient-reported duration of illness		
< 1 month	n (%)	n (%)
1-3 months	n (%)	n (%)
Coexisting medical condition		
Diabetes	n (%)	n (%)
Hypertension	n (%)	n (%)
Stroke	n (%)	n (%)
Heart disease	n (%)	n (%)
Chronic pain	n (%)	n (%)
MDD	n (%)	n (%)
Motor dysfunction	n (%)	n (%)
Surgical history	n (%)	n (%)
ASA physical status	n (%)	n (%)
Charlson's comorbidity scores	Mean (SD)/median (IQR)	Mean (SD)/median (IQR)
Severe depressive symptoms	n (%)	n (%)
Recurrent malignancy	n (%)	n (%)
Preoperative assessment		
PHQ-9	Mean (SD)/median (IQR)	Mean (SD)/median (IQR)

MADRS	Mean (SD)/median (IQR)	Mean (SD)/median (IQR)
GAD-7	Mean (SD)/median (IQR)	Mean (SD)/median (IQR)
HADS	Mean (SD)/median (IQR)	Mean (SD)/median (IQR)
WHODAS 2.0 scores	Mean (SD)/median (IQR)	Mean (SD)/median (IQR)
Z-WHODAS 2.0	Mean (SD)/median (IQR)	Mean (SD)/median (IQR)
Type of surgery	n (%)	n (%)
Other ^a	n (%)	n (%)

Data are shown as the mean (SD)/median (interquartile range) and numbers (%).

Table 2. Primary outcome and Secondary outcomes.

Characteristics	Esketamine group	OR/Difference		P value
		Control group	(95%CI)	
Primary Outcome				
Remission on day 3	n (%)	n (%)	OR (95% CIs)	x
Secondary Outcomes				
NRS Pain scores >3, 0-48 Hours	n (%)	n (%)	OR (95% CIs)	x
Rescue analgesia, 0-48 Hours	n (%)	n (%)	OR (95% CIs)	x
Assessments on POD3				
MADRS	median (IQR)	median (IQR)	D (95% CIs)	x
GAD-7	median (IQR)	median (IQR)	D (95% CIs)	x
HADS	median (IQR)	median (IQR)	D (95% CIs)	x
PHQ-9≥10	n (%)	n (%)	OR (95% CIs)	x
Response	n (%)	n (%)	OR (95% CIs)	x
Assessments on discharge				
MADRS	median (IQR)	median (IQR)	D (95% CIs)	x
GAD-7	median (IQR)	median (IQR)	D (95% CIs)	x
HADS	median (IQR)	median (IQR)	D (95% CIs)	x
PHQ-9≥10	n (%)	n (%)	OR (95% CIs)	x
Response	n (%)	n (%)	OR (95% CIs)	x
Remission	n (%)	n (%)	OR (95% CIs)	x
Length of hospital stay	median (IQR)	median (IQR)	D (95% CIs)	x
Adverse events				
PONV, 0-48 Hours	n (%)	n (%)	OR (95% CIs)	x
Dissociative symptoms (CADSS≥5)	n (%)	n (%)	OR (95% CIs)	x
Psychotic side effects (BPRS 4 items≥5)	n (%)	n (%)	OR (95% CIs)	x
Manic symptoms (YMRS≥5)	n (%)	n (%)	OR (95% CIs)	x
Delirium	n (%)	n (%)	OR (95% CIs)	x
Infection after surgery	n (%)	n (%)	OR (95% CIs)	x
Bleeding events	n (%)	n (%)	OR (95% CIs)	x
Thrombus events	n (%)	n (%)	OR (95% CIs)	x

Figure 1 Flow chart and consort diagram of the study

Figure 2 Primary outcomes and MADRS scores

Figure 3 Subgroup analysis and interactions

10. Reference

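### The SAP's rule replacing missing data with negative results is undefined and not limited to efficacy; read plainly, it counts patients unassessed for harm or pain as event-free

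*SAP*

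**What the plan says.** The Missing Data paragraph of SAP section 8 has four sentences. The second is the rule at issue: "Missing data during the assessment period will be replaced with negative results before breaking blind". The one ahead of it gives a different instruction: "If the amount of missing data is lower than the prescribed attrition rate, which is 10%, the data will drop out". A third sentence gives an open list of alternatives for sensitivity analysis: means, medians, dropouts and negative results. The paragraph then closes on the purpose of the exercise: "The missing data will be reported and analysed to determine their effects on primary efficacy". None of the four defines *negative*, and none confines the replacement rule to an endpoint.

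Several outcomes to which that rule could apply are unfavourable events. SAP section 2 lists "Psychiatric complications: drug-related manic, psychotic, and dissociative symptoms during the first 3-day postoperative period" among the safety endpoints and, among the secondary ones, "The rate of moderate-to-severe pain during the first postoperative 3 days". Table 2 in SAP section 9 scores dissociation, psychotic effects and mania as events at a score of 5 or more, and pain as an event above 3. It also lists delirium and PHQ-9 of 10 or more.

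The Safety analysis paragraph of section 9 has no missing-data rule of its own. It says "Safety endpoints will be assessed in the total population", whereas section 7 assigns safety to the modified intent-to-treat population.

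The protocol (Statistical analysis) plans mean or median imputation, last observed assessment and multiple imputation, with sensitivity analyses across them. It contains no negative-result rule.

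**The concern.** One rule works in opposite directions for different outcomes. A missing MADRS score set to non-remission lowers that arm's success rate, which is the usual cautious choice. A missing CADSS, BPRS, YMRS or pain score set to a negative screen lowers that arm's harm rate, which is not cautious.

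The SAP makes psychiatric and other safety events an objective. The protocol's Discussion says the safety of esketamine as an antidepressant during surgery is unknown and that psychotic, manic and dissociative symptoms may become more frequent. If unassessed patients are counted as event-free, these rates are too low. If the missing share differs between arms, the comparison between arms is biased as well. No listed sensitivity analysis would show this, because none counts a missing harm score as an event.

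**Working it through.** **Inputs.** From the SAP: 564 patients at 1:1, so 282 per arm, and 10% attrition. The stated total reproduces: 506 / 0.90 = 562.2, which rounds up to 563, or 564 as an even number. The point challenges no stated figure. The documents give no harm rates and no missing shares by arm, so those below are assumptions.

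**Meaning of *negative* by outcome.**

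| Outcome | Plain reading of *negative* | Effect on the reported rate |
|---|---|---|
| Remission, response | not achieved | cautious |
| Mania, psychosis, dissociation, delirium | event absent | understates harm |
| Pain above 3 | event absent | understates pain |
| PHQ-9 of 10 or more | below the cut-off | understates depressive symptoms |

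**Effect within an arm.** Let p be the rate among assessed patients and m the share missing. Counting the missing as event-free gives p(1 − m). At m = 0.10, assumed rates of 10% and 5% become 9.0% and 4.5%. The risk difference goes from 5.0 to 4.5 points and the risk ratio stays at 2.00.

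**Effect between arms.** If missingness is unrelated to outcome, the risk ratio is multiplied by (1 − m on esketamine) / (1 − m on placebo). The odds ratio, which the SAP plans to report for safety, follows from the same rates.

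| Assumed true rates | Missing, esketamine / placebo | Reported rates | Difference (points) | Risk ratio | Odds ratio |
|---|---|---|---|---|---|
| 10% vs 5% | 0 / 0 | 10% vs 5% | 5.0 | 2.00 | 2.11 |
| 10% vs 5% | 10% / 10% | 9.0% vs 4.5% | 4.5 | 2.00 | 2.10 |
| 10% vs 5% | 15% / 5% | 8.5% vs 4.75% | 3.75 | 1.79 | 1.86 |
| 10% vs 5% | 5% / 15% | 9.5% vs 4.25% | 5.25 | 2.24 | 2.36 |
| 40% vs 30% (pain-like) | 15% / 5% | 34% vs 28.5% | 5.5 (true 10) | 1.19 (true 1.33) | 1.29 (true 1.56) |

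With equal arms, 15% and 5% average 10%, which is not below the drop threshold if that is judged over both arms together. The SAP does not say whether it is judged overall, by arm or by endpoint.

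**The competing readings on one example.** Take 10% missing and 2% events among assessed patients:

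- missing dropped: 2.0%
- *negative* read as absent: 0.90 × 2% = 1.8%
- *negative* read as unfavourable: 1.8% + 10% = 11.8%

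**What the rule does not cause.** Suppose unassessed patients have a 30% event rate (assumed).

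- 5% missing, 5% among assessed: true rate 0.95 × 5% + 0.05 × 30% = 6.25%. The rule reports 4.75%, which is 24% low. Assessed-only reports 5.0%, still 20% low.
- 10% missing, 2% among assessed: true rate 0.90 × 2% + 0.10 × 30% = 4.8%. The rule reports 1.8%, which is 62.5% low. Assessed-only reports 2.0%, still 58% low.

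The rule's own share is 0.25 and 0.2 points. The rest comes from the assumed 30%.

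**Primary outcome.** At 10% missing in both arms, the assumed 19.3% and 10% become 17.4% and 9.0% on 282 per arm. Fixed-sample power is about 84%, as it is for the 253 per arm left if the missing are dropped. Keeping the rule for remission does no harm in this scenario.

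**The case against.** The strongest objection is the sentence just before the rule. If data are dropped whenever less than 10% are missing, unassessed patients are left out at low missingness and nobody is counted as event-free. A reader might infer that the SAP certainly counts every unassessed patient as free of harm. The documents do not support that: the two sentences are unreconciled and *negative* is undefined. What remains is that the second sentence carries no threshold, so its plain reading is open to whoever runs the analysis.

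*Negative* could mean unfavourable. For remission both meanings agree. For harms they are opposite, so this shows that a definition is needed.

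The paragraph ends on primary efficacy, which makes an efficacy-only intention plausible. That sentence describes what the missing-data analysis is for; it does not limit the replacement rule, and harms have no other rule.

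Some protection exists. The sensitivity list is open-ended and includes dropouts, which amounts to an assessed-only analysis, although its stated purpose is primary efficacy. Missing data are to be recorded by centre. Section 7 removes from the modified intent-to-treat population patients who cannot be followed up because of surgical complications such as aphasia or coma, but section 9 places safety in the total population, so that exclusion may not apply.

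Neither document says that unassessed patients are more likely to have had the event. That is an assumption.

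**Conclusion.** The point holds as a defect of definition and scope with a known direction. On its plain reading the rule understates harm, pain and PHQ-9 event rates by the factor (1 − m), and it conflicts both with the under-10% drop rule and with the protocol's imputation plan.

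The size is modest when missingness is equal: at 10% missing, one tenth off rates and risk differences, with no change in the risk ratio. It matters more when missingness is unequal. On assumed true rates of 10% and 5%, a 15% / 5% split turns a risk ratio of 2.00 into 1.79, and the reverse split gives 2.24, so the bias can go either way. These results rest on assumed rates and missing shares, and on missingness unrelated to outcome.

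A reader might infer that the rule hides a quarter or more of the harm. The documents do not support that. A gap of that size needs a much higher event rate in unassessed patients, and most of it would remain in an assessed-only analysis.

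**What to change.** Amend the Missing Data paragraph of SAP section 8, before unblinding if that is still possible:

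1. Limit the replacement rule to remission and response, and write it as *not remitted / not responded*.
2. State how that rule fits with the under-10% drop rule: which one governs, and whether the 10% is judged overall, by arm or by endpoint. State whether the protocol's mean or median, last-observation and multiple imputation are kept as sensitivity analyses or superseded.
3. For safety, pain and PHQ-9 of 10 or more, report events over patients assessed, with the number missing in each arm.
4. Add one sensitivity analysis for these outcomes that counts missing as an event. Assessed-only results do not correct for missingness related to the event, and this analysis gives the upper limit.
5. Name one safety population, so that the denominators in items 3 and 4 are fixed.

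The cost is a few sentences and one extra table. Reported harm rates may be slightly higher. The replacement rule stays available for the primary outcome.
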